### **6.5.1. Palliative Medicine and Supportive Care for LY3475070**

The need for any form of radiotherapy (including palliative) in Cycles 1 and 2 will be cause for early discontinuation from the study. In Cycle 3 and beyond, palliative radiotherapy will be allowed.

In addition, any disease progression requiring other forms of specific antitumor therapy will also necessitate early discontinuation from the study. Appropriate documentation for all forms of premedications, supportive care, and concomitant medications must be captured on the case report form.

Patients should receive full supportive care. The use of granulocyte-colony stimulating factor (G-CSF) is permitted at the discretion of the investigator based on American Society for Clinical Oncology (ASCO) (Smith et al. 2015) and European Society for Medical Oncology (Crawford et al. 2009) guidelines.

If clinically indicated at any time during the study, erythropoietin and packed red blood cell transfusions may be used according to ASCO guidelines (Rizzo et al. 2008). Prophylactic antibiotic treatment should be consistent with ASCO guidelines (Flowers et al. 2013).

All concomitant medications should be recorded throughout the patient's participation in the study.

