The actual time of dose administrations will be transcribed and provided to the sponsor.

If LY3475070 is discontinued, pembrolizumab may be continued alone for up to 2 years (35 cycles). Conversely, if pembrolizumab is discontinued, LY3475070 may be continued alone.

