- Investigational agents other than pembrolizumab
- Radiation therapy

Note: Radiation therapy to a symptomatic solitary lesion or to the brain may be allowed at the investigator's discretion.

- Live vaccines within 30 days prior to the first dose of study treatment and while participating in the study. Examples of live vaccines include, but are not limited to, the following: measles, mumps, rubella, varicella/zoster, yellow fever, rabies, BCG, and typhoid vaccine. Seasonal influenza vaccines for injection are generally killed virus vaccines and are allowed; however, intranasal influenza vaccines are live attenuated vaccines and are not allowed.
- Systemic glucocorticoids for any purpose other than to modulate symptoms from an AE that is suspected to have an immunologic etiology. The use of physiologic doses of corticosteroids may be approved after consultation with the Lilly CRP/CRS.

Note: Inhaled steroids are allowed for management of asthma.

Participants who, in the assessment of the investigator, require the use of any of the aforementioned treatments for clinical management should be removed from the study.

All treatments that the investigator considers necessary for a participant's welfare may be administered at the discretion of the investigator in keeping with the community standards of medical care.

All concomitant medication will be recorded on the eCRF including all prescription, over-the-counter products, herbal supplements, and IV medications and fluids. If changes occur during the study period, documentation of drug dosage, frequency, route, and date should also be included on the eCRF.

All concomitant medications received within 28 days prior to the first dose of study treatment and up to 90 days after the last dose of study treatment should be recorded. Concomitant medications administered up to 90 days after the last dose of study treatment should be recorded for SAEs and events of clinical interest (Section 8.3.7).

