## 6.6. Dose Modification

### 6.6.1. Dose Modification and Toxicity Management of LY3475070 for Non-immune-mediated AEs Associated with LY3475070 and/or in Combination with Pembrolizumab

Patient may receive up to 2 dose reductions for AEs attributed to LY3475070. LY3475070 treatment may be interrupted, dose reduced or discontinued due to toxicity per the tables below.

Patients who have dose delays of more than 14 days, unless a different duration is specified in the above table, should permanently discontinue from the study.

Due to its MOA, LY3475070 may induce irAEs that could affect any organ of the body. Previous trials with agents inhibiting the adenosine pathway have not reported irAEs to the same incidence rate as seen with other check point inhibitors such as CTLA4 or PD-1/L1. From the ongoing A2AR antagonist single agent data only rash/pruritus, and elevated LFTs have been reported. In the event other irAEs occur please consult the table provided in Section 6.6.1.2 for management of irAEs.

Related AEs	Toxicity Grade or Conditions (CTCAE v5.0)	Action Taken to Therapy	AE Management	Monitor and Follow-up
Non hematologic				
Acneiform Rash	Grade 1	Continue treatment	Initiate topical prophylactic antibiotic (e.g., clindamycin). Consider using low potency topical steroids (e.g., hydrocortisone 2.5%)	Monitor for worsening signs and symptoms.
	Grade 2	Withhold therapy until $\leq$ Grade 1 (for recurrent Grade 2, or toxicity lasting more than 2 weeks proceed as Grade 3). If immune mediated rash is suspected see below table for management of immune mediated AE's).	Initiate oral antibiotic (e.g., doxycycline). Initiate low potency topical steroid, if not already started. Consider skin biopsy if immune mediated toxicity is suspected	Monitor for worsening signs and symptoms weekly

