### **7.1. Discontinuation of Study Intervention**

Discontinuation of study treatment does not represent withdrawal from the study.

Participants may discontinue study treatment at any time for any reason or be discontinued from the study treatment at the discretion of the investigator should any untoward effect occur. In addition, a subject may be withdrawn by the investigator or the sponsor if enrollment into the trial is inappropriate, the trial plan is violated or for administrative and/or other safety reasons.

A subject must be discontinued from the trial for the following reasons:

- the participant or the participant's designee, for example, parents or legal guardian requests to discontinue investigational product.
- the subject is lost to follow -up

A subject must be discontinued from trial treatment but continue to be followed for any of the following reasons:

- the patient becomes pregnant during the study
- the patient is significantly noncompliant with study procedures and/or treatment
- disease progression. Disease progression should be confirmed per iRECIST 4 to 8 weeks after site-assessed first radiologic evidence of PD in clinically stable participants. Participants, who have unconfirmed disease progression may continue on treatment at the discretion of the investigator until progression per iRECIST. Any participant deemed clinically unstable should be discontinued from study treatment at first radiologic evidence of PD and is not required to have repeat tumor imaging for confirmation of PD by iRECIST.
- unacceptable toxicity
- the patient, for any reason, requires treatment with another therapeutic agent that has been demonstrated to be effective for treatment of the study indication. Discontinuation from study invention will occur prior to introduction of the new agent.
- Recurrent Grade 2 pneumonitis
- Discontinuation of treatment may be considered for participants who have attained a confirmed complete response (CR) and have been treated for at least 8 cycles (at least 24 weeks), receiving [for monotherapy: at least 2 doses of pembrolizumab; for

combination treatment: 2 cycles of the combination including 2 doses of pembrolizumab and at least 75% of the planned doses of LY3475070] beyond the date when the initial CR was declared.

- Pembrolizumab will be discontinued after completion of approximately 2 years of treatment with pembrolizumab (completion of 35 treatments with pembrolizumab).  

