## **7.2. Participant Discontinuation/Withdrawal from the Study**

Participants will be discontinued in the following circumstances:

- enrollment in any other clinical study involving an investigational product or enrollment in any other type of medical research judged not to be scientifically or medically compatible with this study
- participation in the study needs to be stopped for medical, safety, regulatory, or other reasons consistent with applicable laws, regulations, and good clinical practice (GCP)
- subject decision
  - the participant or the patient's designee, for example, parents or legal guardian requests to be withdrawn from the study
- the patient becomes pregnant during the study. See Section 8.3 regarding regulatory reporting requirements on fetal outcome.
- Participants discontinuing from the study prematurely for any reason should complete AE and other safety follow-up per Section 1.3 (Schedule of Activities), Section 8.3 (Adverse Events and Serious Adverse Events), and Section 8.2 (Safety Assessments) of this protocol.

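### Protocol Sections 6.5, 6.5.1, 6.6.1, 7.1 and 7.2 take some patients out of the study rather than only off treatment, against Section 7.1's own follow-up rule, and this puts Phase 1b survival follow-up at risk

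*Protocol*

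**What the plan says.** Section 7.1 of the protocol opens with the rule "Discontinuation of study treatment does not represent withdrawal from the study". One of its lists is headed "A subject must be discontinued from trial treatment but continue to be followed for any of the following reasons", and that list includes disease progression, pregnancy and the need for another agent effective in the study indication.

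Other current text sends the same or similar patients out of the study:

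- **Section 6.5.1:** "any disease progression requiring other forms of specific antitumor therapy will also necessitate early discontinuation from the study". The need for radiotherapy in Cycles 1 and 2 has the same consequence.
- **Section 6.5:** participants who "require the use of any of the aforementioned treatments for clinical management should be removed from the study". The treatments listed include chemotherapy, biological therapy and immunotherapy.
- **Section 6.6.1:** patients with dose delays of more than 14 days, "unless a different duration is specified in the above table, should permanently discontinue from the study". Section 6.1 allows pembrolizumab to go on alone after LY3475070 is stopped.
- **Section 7.2:** the grounds for leaving the study include "the patient becomes pregnant during the study. See Section 8.3 regarding regulatory reporting requirements on fetal outcome".
- **Section 7.1:** the list of reasons for leaving the trial includes a participant or designee who only asks to stop the drug ("parents or legal guardian requests to discontinue investigational product").

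The Schedule of Activities (Section 1.3) collects survival and post-treatment anticancer therapy in long-term follow-up. Its footnote b ends that follow-up at death, study withdrawal or loss to follow-up. Section 9.4.3.3 censors OS at the last date known alive for patients withdrawn from the study. SAP Section 6.7 plans Kaplan-Meier OS but gives no OS definition of its own, so the protocol rule applies.

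**The concern.** OS is a Phase 1b secondary endpoint in protocol Section 3 and SAP Section 4.2. Most deaths in these populations will come after progression, and many will come after a further line of therapy. If needing that therapy ends study participation, survival is lost for the patients who supply much of the late follow-up.

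The censoring would also be informative. It is triggered by progression, which raises the hazard of death, and by fitness for another treatment, which lowers it. Kaplan-Meier assumes that censored patients have the same outlook as those still at risk, and neither trigger respects that. Two sites following different sections would censor the same kind of patient differently.

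**Working it through.** **Step 1. Set the rules side by side.**

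| Situation | Stays in follow-up | Leaves the study |
|---|---|---|
| Progression or need for another anticancer therapy | 7.1, second list | 6.5, 6.5.1 |
| Pregnancy | 7.1, second list | 7.2 |
| Request only to stop the drug | 7.1, opening and closing text | 7.1, first list |
| Dose delay over 14 days | 7.1 opening; 6.1 (pembrolizumab alone) | 6.6.1 |

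The title of Section 7.2 treats study discontinuation and study withdrawal as one thing. Footnote b of the schedule and the OS rule in 9.4.3.3 therefore apply to anyone discontinued from the study. Section 7.2 names only AE and other safety follow-up for them.

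**Step 2. Illustrate the size.** The documents give no OS event count, power or survival assumption, so there is no plan figure to reproduce and every input here is assumed. Base inputs: median time to progression or death 2.5 months, 15% of first events are deaths, exponential times, 24 months of follow-up, and half of progressors receive further therapy and are removed. Median post-progression survival is either 10 months with further therapy and 3 months without, or 7 months for both.

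Rates: a = ln 2 / 2.5 = 0.2773 per month; b = ln 2 / (post-progression median).

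P(dead by 24 months, given progression first) = 1 − (a·e^(−24b) − b·e^(−24a)) / (a − b), which is 0.748 for a 10-month median, 0.983 for 3 months and 0.856 for 7 months. Deaths as first event contribute 0.15 × (1 − e^(−24a)) = 0.150. Removed and non-removed progressors each make up 0.85 × 0.5 = 0.425.

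Deaths per 40 patients, 10/3-month case:

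- Full follow-up: 40 × (0.150 + 0.425 × 0.748 + 0.425 × 0.983) = 35.4
- Censored at progression: 40 × (0.150 + 0.425 × 0.983) = 22.7
- Censored 3 months after progression: add 40 × 0.425 × (1 − e^(−3b)) = 40 × 0.425 × 0.188 = 3.2, giving 25.9

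The last line allows for the 90-day safety visit and assumes that treatment stops at progression. Kaplan-Meier medians come from simulating 1,000,000 patients.

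| Post-progression median | Censoring of removed patients | Deaths per 40 | KM median OS (months) | Shift |
|---|---|---|---|---|
| 10 / 3 | none | 35.4 | 7.95 | – |
| 10 / 3 | at progression | 22.7 | 7.14 | −0.8 |
| 10 / 3 | progression + 3 months | 25.9 | 7.53 | −0.4 |
| 7 / 7 | none | 35.1 | 9.35 | – |
| 7 / 7 | at progression | 20.5 | 10.21 | +0.9 |
| 7 / 7 | progression + 3 months | 24.9 | 9.65 | +0.3 |

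The sign changes for a clear reason. If removed patients have the better outlook, those left behind pull the curve down. If outlook after progression is equal, removed patients are implicitly replaced by an at-risk group that still includes progression-free patients, and the curve goes up.

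**Step 3. Vary the inputs.** Take 10% of first events as deaths, median time to first event 3 to 6 months, and post-progression median 6 to 9 months, equal in both groups. With half of progressors removed, 27 to 36 deaths per 40 fall to about 16 to 20 if censored at progression, and the median rises by 1.3 to 3.1 months. Censored 3 months later, 19 to 25 deaths remain and the median rises by 0.5 to 1.8 months. The loss of deaths appears in every scenario; the size and direction of the median shift do not carry over.

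**The case against.** The strongest reply is that the protocol does direct follow-up to continue. Section 7 opens by requiring schedule-based follow-up for patients who discontinue during the treatment period. Section 7.1 closes by requiring it for anyone stopping the drug early for whatever reason. The schedule collects next-line therapy, which makes sense only if patients stay in after starting it. Section 6.5 also says, a little before the removal sentence, that a prohibited medication may require stopping trial therapy, which is a treatment-level rule. Section 7.3 has vital status sought for all randomized participants, including from public sources.

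Most of this stands. A reader might infer that every patient fit for a next line will certainly be censored for OS at progression; the documents do not support that, because a site applying Sections 7 and 7.1 would keep following. The reply does not remove the conflict, however. The schedule that those sections point to itself stops long-term follow-up at study withdrawal. The vital-status provision sits under loss to follow-up and does not reach Cohort E, which has up to 40 patients and is not randomized.

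A reader might also infer serious damage to PFS. Section 8.1.1 continues imaging in patients who stop without confirmed progression until progression, new therapy or withdrawal of consent, and PFS is censored at new anticancer therapy in any case. That largely protects it. ORR is little affected, since best response is determined before progression.

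Finally, the possible bias is modest beside sampling error. In the 10/3-month case, the median for 40 fully followed patients has a 95% sampling range of about 5.2 to 11.0 months.

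**Conclusion.** The inconsistency is real and lies in current text. Read literally, it ends survival follow-up for patients whom Section 7.1 means to keep, and it censors OS in a way related to prognosis. Whether that happens depends on which section a site follows, so it is a risk and not an established loss.

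On the base assumptions with half of progressors removed, about 35 deaths per 40 fall to roughly 23 to 26 (21 to 25 if post-progression survival is equal), and median OS moves by 0.3 to 0.9 month, down or up. The longer-survival inputs give larger upward shifts. A reader might infer that OS would be overstated; the direction is in fact not determined.

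The endpoint affected is descriptive. OS is secondary in the objectives, analysed under exploratory analyses in Section 9.4.3.3, and has no test or event target. Safety and ORR, the Phase 1b primary endpoints, do not depend on it. The wording deserves correction because survival data not collected may be hard to recover, but it does not undermine the trial's primary conclusions.

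**What to change.** Leave all treatment-stopping triggers as they are and change only what follows them.

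- **Sections 6.5 and 6.5.1:** replace removal or discontinuation from the study with *discontinued from study treatment and followed per the SoA, including survival follow-up*.
- **Section 7.1:** move the request to stop investigational product from the leave-the-trial list to the list of patients who continue to be followed.
- **Sections 7.1 and 7.2:** state that survival follow-up continues unless consent is withdrawn or the patient is lost to follow-up. Keep 7.2's other grounds, such as enrolment in another study or medical, safety or regulatory reasons.
- **Sections 6.6.1 and 6.1:** reconcile the 14-day delay wording with the provision for pembrolizumab alone. The sponsor must decide the clinical rule; this review takes no view on it.
- **Pregnancy entries in 7.1 and 7.2:** reconcile them, and keep the pointer to fetal-outcome reporting.

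The cost is wording in five protocol sections (6.1 too, if the reconciliation touches it). The survival contact is already scheduled every 90 days and may be made by telephone, so the added burden is small.

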## 6.6. Dose Modification

### 6.6.1. Dose Modification and Toxicity Management of LY3475070 for Non-immune-mediated AEs Associated with LY3475070 and/or in Combination with Pembrolizumab

Patient may receive up to 2 dose reductions for AEs attributed to LY3475070. LY3475070 treatment may be interrupted, dose reduced or discontinued due to toxicity per the tables below.

Patients who have dose delays of more than 14 days, unless a different duration is specified in the above table, should permanently discontinue from the study.

Due to its MOA, LY3475070 may induce irAEs that could affect any organ of the body. Previous trials with agents inhibiting the adenosine pathway have not reported irAEs to the same incidence rate as seen with other check point inhibitors such as CTLA4 or PD-1/L1. From the ongoing A2AR antagonist single agent data only rash/pruritus, and elevated LFTs have been reported. In the event other irAEs occur please consult the table provided in Section 6.6.1.2 for management of irAEs.

Related AEs	Toxicity Grade or Conditions (CTCAE v5.0)	Action Taken to Therapy	AE Management	Monitor and Follow-up
Non hematologic				
Acneiform Rash	Grade 1	Continue treatment	Initiate topical prophylactic antibiotic (e.g., clindamycin). Consider using low potency topical steroids (e.g., hydrocortisone 2.5%)	Monitor for worsening signs and symptoms.
	Grade 2	Withhold therapy until $\leq$ Grade 1 (for recurrent Grade 2, or toxicity lasting more than 2 weeks proceed as Grade 3). If immune mediated rash is suspected see below table for management of immune mediated AE's).	Initiate oral antibiotic (e.g., doxycycline). Initiate low potency topical steroid, if not already started. Consider skin biopsy if immune mediated toxicity is suspected	Monitor for worsening signs and symptoms weekly
	Grade 3	Withhold therapy until $\leq$ grade 1 then dose reduce LY3475070 (if rash worsens or does not improve in two weeks permanently discontinue) If Stevens–Johnson syndrome or toxic epidermal necrosis permanently discontinue patient	Initiate oral antibiotic (e.g., doxycycline). Initiate systemic corticosteroid (e.g., prednisone 0.5 mg/kg daily (maximum dose, 40 mg). Consider dermatology consultation.	Monitor for worsening signs and symptoms weekly until improvement to $\leq$ Grade 1. Resume LY treatment with 1 DL reduction. If rash does not improve or worsens after 2 weeks of treatment, discontinue LY permanently. If Stevens–Johnson syndrome or toxic epidermal necrolysis is suspected, discontinue permanently.
	Grade 4	Permanently discontinue	Initiate oral antibiotic (e.g., doxycycline). Initiate systemic corticosteroid (e.g., prednisone 0.5 mg/kg daily (maximum dose, 40 mg). Consider dermatology consultation.	
Diarrhea	Grade 1	Continue LY3475070 treatment. Start loperamide 4 mg initially, followed by 2 mg every 4 hours or after each stool.	Consider discontinue of lactose containing products	

Related AEs	Toxicity Grade or Conditions (CTCAE v5.0)	Action Taken to Therapy	AE Management	Monitor and Follow-up
	Grade 2	Continue LY3475070 treatment if Grade 2 diarrhea lasts <48 hours. Hold LY3475070 treatment if Grade 2 diarrhea lasts ≥48 hrs treatment until resolution to ≤ Grade 1.	Start loperamide 4 mg initially, followed by 2 mg every 4 hours or after each stool. Encourage oral hydration. If immune mediated colitis is suspected, consider GI consultation and biopsy.	
	Grade 3	Hold LY3475070 until resolution to Grade ≤ 1. Resume LY at 1 DL lower upon recovery.	If not already done, start loperamide 4 mg initially, followed by 2 mg every 4 hours or after each stool. Consider hospitalization for symptom and fluid management and GI consultation.	
	Grade 4	Permanently discontinue LY3475070 treatment	Consider hospitalization for symptom and fluid management, hydration and GI consultation.	
AST/ALT elevation or Increased bilirubin	Grade 1	Continue LY3475070 treatment	Review concomitant medications and alcohol use	
	Grade 2	Continue treatment if immune mediated transaminitis is not suspected. Hold LY3475070 if immune mediated transaminitis is suspected (see below table for management of immune mediated AE's).	Review concomitant medications and alcohol use Consider hepatology consultation and rule out biliary obstruction due to disease progression Consider biopsy if immune mediated transaminitis suspected.	Monitor LFTs every 2-5 days until ≤Grade 1 (see protocol section 8.2.1.1)
	Grade 3	Hold LY3475070 until ≤Grade 1. Resume LY3475070 treatment at 1 DL lower if the patient has no evidence of drug induced hepatocellular injury. Patients with evidence of drug induced hepatocellular injury (i.e., transaminase ≥3XULN and total bilirubin ≥2XULN should	Review concomitant medications and alcohol use Consider hepatology consultation	Monitor LFTs every 2-5 days until ≤Grade 1 (see protocol section 8.2.1.1)

Related AEs	Toxicity Grade or Conditions (CTCAE v5.0)	Action Taken to Therapy	AE Management	Monitor and Follow-up
		permanently discontinue LY3475070 treatment.		
	Grade 4	Permanently discontinue LY3475070 treatment	Review concomitant medications and alcohol use Consider hepatology consultation.	Monitor LFTs every 2-5 days until ≤Grade 1 (see protocol section 8.2.1.1).
CCI				
Fatigue	Grade 1	Continue treatment	Manage per routine clinical practice and/or institutional guidelines	
	Grade 2	Continue treatment	Manage per routine clinical practice and/or institutional guidelines	
	Grade 3	Withhold LY3475070 until resolution ≤ grade 1, if resolved within 7 days then resume treatment.	Manage per routine clinical practice and/or institutional guidelines	

Related AEs	Toxicity Grade or Conditions (CTCAE v5.0)	Action Taken to Therapy	AE Management	Monitor and Follow-up
		If grade 3 persist over 7 days then dose reduce one level. If recurrence after continuing treatment dose reduce one level.		
Non-Hematologic Toxicity 	Grade 1	Continue LY3475070 treatment	Manage per routine clinical practice and/or institutional guidelines	
	Grade 2	Withhold LY3475070 treatment until resolution to ≤ grade 1 for recurrent Grade 2, or toxicity lasting more than 2 weeks proceed as Grade 3	Manage per routine clinical practice and/or institutional guidelines	
	Grade 3 or recurrent Grade 2	Withhold treatment until resolution to ≤ grade 1 and then reduce dose one level.	Manage per routine clinical practice and/or institutional guidelines	
	Grade 4	Permanently discontinue	Manage per routine clinical practice and/or institutional guidelines.	
Hematologic toxicity				
Neutropenia	Grade 1	Continue treatment		
	Grade 2	Continue treatment		
	Grade 3	Withhold LY3475070 until resolution ≤ grade 1 for recurrent Grade 3, or toxicity lasting more than 2 weeks proceed as grade 4.  If febrile neutropenia then dose reduce one level upon resolution ≤ grade 1	If patient is above 38.0° C on 2 separate occasions and or associated with signs or symptoms of sepsis start intravenous in accordance with the local hospital neutropenic sepsis guidelines G-CSF support may be given as deemed appropriate by the physician per institutional guidelines	Perform CBC weekly ≤Grade 3
	Grade 4	Withhold LY3475070 until resolution ≤ grade 1 then resume at one reduced DL. If neutropenia is longer than 5 days discontinue patient	If patient is above 38.0° C on two separate occasions and or associated with signs or symptoms of sepsis start intravenous in accordance with the local hospital neutropenic sepsis guidelines.	Perform CBC weekly ≤Grade 3

Related AEs	Toxicity Grade or Conditions (CTCAE v5.0)	Action Taken to Therapy	AE Management	Monitor and Follow-up
			G-CSF support may be given as deemed appropriate by the physician per institutional guidelines.	
Anemia	Grade 1	Continue dose		
	Grade 2	Continue dose		
	Grade 3	Withhold LY3475070 until resolution ≤ grade 1 then resume at one reduced DL	Blood transfusions as per local institutional guidelines	Perform CBC weekly ≤Grade 3
	Grade 4	Discontinue treatment	Blood transfusions as per local institutional guidelines	
Thrombocytopenia	Grade 1 (LLN > 75,000 mcL)	Continue dose		
	Grade 2 (75,000>25,000)	Continue dose		
	Grade 3 (<25,000 mcL) with significant bleeding	Withhold LY3475070 until resolution ≤ Grade 1 and resume treatment. If associated with bleeding, or Grade 3 reoccurs, then resume at one reduced DL. If thrombocytopenia Grade 3 reoccurs at lower DL discontinue patient.	Platelet transfusion per local institutional guidelines.	Perform CBC weekly ≤Grade 3.
	Grade 4 life threatening spontaneous bleeding	Permanently discontinue.	Platelet transfusion per local institutional guidelines	

Abbreviations: CBC = complete blood count; CCI; CCI; G-CSF  
= granulocyte colony-stimulating factor; LFTs = liver function tests; CCI.

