## 6.5. Concomitant Therapy

At baseline, record prior and concurrent medications. Record all premedication, supportive care, and concomitant medication continuously at every visit and throughout the study.

The Lilly CRP/CRS should be contacted if there are any questions regarding concomitant or prior therapy. Patients with metastatic CRPC may continue with luteinizing hormone-releasing hormone analogue for testosterone suppression. Zoledronic acid or denosumab given for bone support is allowed to be continued if started 1 week prior to study treatment dosing. However, zoledronic acid or denosumab should not be initiated, especially in metastatic CRPC patients, after study treatment has commenced. No other chemotherapy, immunotherapy, herbal supplements and/or herbal drugs intended to treat cancer, or experimental drugs will be permitted while the patients are in this study.

CCI

If patients can't be switched to alternative therapy Lilly CRP/CRS must be consulted. For a list please consult Appendix 5. Immune-suppressive glucocorticosteroids other than to treat treatment related irAE are also prohibited.

Administration of live vaccines is prohibited during the study and for 3 months following the final dose of study drug. Any medication or vaccine (including over-the-counter or prescription medicines, vitamins, and/or herbal supplements) that the participant is receiving at the time of enrollment or receives during the study must be recorded along with:

- Reason for use
- Dates of administration including start and end dates

Medications or vaccinations specifically prohibited in the exclusion criteria are not allowed during the ongoing trial. If there is a clinical indication for any medication or vaccination specifically prohibited during the trial, discontinuation from trial therapy or vaccination may be required. The investigator should discuss any questions regarding this with the Sponsor. The final decision on any supportive therapy or vaccination rests with the investigator and/or the participant's primary physician. However, the decision to continue the participant on study treatment requires the mutual agreement of the investigator, Lilly CRP/CRS, and the participant.

Listed below are specific restrictions for concomitant therapy or vaccination during the course of the study:

- Antineoplastic systemic chemotherapy or biological therapy
- Immunotherapy not specified in this protocol
- Chemotherapy not specified in this protocol

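### For Grade 3 acneiform rash not suspected to be immune-mediated, protocol Section 6.6.1 directs prednisone and a restart at a lower dose, while Section 6.5 bars that steroid and calls for removal; the scope is narrow and the point minor

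*Protocol*

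**What the plan says.** **Protocol Section 6.6.1** is headed for adverse events that are not immune-mediated. In its acneiform rash rows:

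- Grade 2: withhold, with an oral antibiotic and a low-potency topical steroid. The action column adds "for recurrent Grade 2, or toxicity lasting more than 2 weeks proceed as Grade 3" and "If immune mediated rash is suspected see below table for management of immune mediated AE's".
- Grade 3: withhold until Grade 1 or less. The management column says "Initiate systemic corticosteroid (e.g., prednisone 0.5 mg/kg daily (maximum dose, 40 mg". The follow-up column says "Resume LY treatment with 1 DL reduction". The exit rule is "if rash worsens or does not improve in two weeks permanently discontinue".
- Grade 4: the same prednisone text, with permanent discontinuation.

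**Protocol Section 6.5** deals with steroids twice. The narrative says "Immune-suppressive glucocorticosteroids other than to treat treatment related irAE are also prohibited". The later list of restrictions bars systemic glucocorticoids unless they are given for an event suspected to be immunologic, and allows physiologic doses after consulting the sponsor. A sentence after the list says that participants who need any listed treatment should be removed from the study. Between the two statements, a paragraph on prohibited medication says that "discontinuation from trial therapy or vaccination may be required", and makes staying on study treatment depend on agreement among the investigator, the sponsor's physician or scientist, and the patient.

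Neither section refers to the other on steroids for rash.

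**The concern.** A site with a patient whose Grade 3 rash is not thought to be immune has two operative instructions that cannot both be followed. Under the toxicity table it gives prednisone and restarts at the lower dose. Under the concomitant-therapy section, read as written, the need for that prednisone is a reason to take the patient off the study.

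What is at stake is consistent handling across sites and, in a few patients, experience at the reduced dose. Protocol Section 6.1.2 names dose adjustments and chronic intolerance among the inputs to the recommended Phase 2 dose. There is also a reporting side. SAP Section 6.11 summarises violations in categories that include excluded treatments and continuing after withdrawal criteria are met, so a site that correctly follows the rash row could be logged as deviating.

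**Working it through.** The plan states no figure on this point. The check is a comparison of text, plus one small dose calculation.

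**Step 1. Which rash does the row cover?** The heading of Section 6.6.1 and the Grade 2 routing ("If immune mediated rash is suspected see below table for management of immune mediated AE's") both point to rash not suspected to be immune. The Grade 3 row does not repeat the routing.

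**Step 2. Where do the instructions collide?**

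| Case | Section 6.6.1 | Section 6.5 | Conflict over staying on treatment? |
|---|---|---|---|
| Rash suspected to be immune | Go to the irAE table (explicit at Grade 2) | Steroid allowed | No |
| Grade 3, not suspected immune, improving within two weeks | Prednisone, then restart one level lower | Steroid barred; remove | **Yes** |
| Grade 3, worse or no better at two weeks | Permanent stop | Remove | No |
| Grade 4, Stevens-Johnson syndrome or toxic epidermal necrolysis | Permanent stop | Remove, if not suspected immune | No |

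Two further limits apply. In Phase 1a, a Grade 3 rash inside the 28-day window would usually be a DLT, and Section 6.1.1.1 then ends study treatment. The general delay rule in Section 6.6.1 ("Patients who have dose delays of more than 14 days, unless a different duration is specified in the above table, should permanently discontinue") may also end treatment if the hold runs past 14 days. The collision is therefore mainly in Phase 1b, or in Phase 1a after day 28.

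**Step 3. Does any clause in Section 6.5 remove it?**

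- *Agreement clause.* It offers a way to continue, case by case. It does not say that steroid use under the toxicity table is acceptable, and the removal sentence later in the section carries no reference to it.
- *Welfare clause.* It lets the investigator give treatment the patient needs. It says nothing about whether that patient stays on study.
- *Physiologic-dose approval.* This depends on the dose, checked next.

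**Step 4. Is the directed dose physiologic?** Inputs: 0.5 mg/kg daily capped at 40 mg (Section 6.6.1), and the 10 mg/day of prednisone that exclusion criterion 25 uses as its example of the supraphysiologic threshold (Section 5.2). Body weights are assumed.

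Daily dose = min(0.5 × weight, 40):

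- 50 kg: 0.5 × 50 = 25 mg
- 60 kg: 0.5 × 60 = 30 mg
- 70 kg: 0.5 × 70 = 35 mg
- 80 kg and above: 40 mg, since 40 / 0.5 = 80 kg

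Against 10 mg/day this is 25/10 = 2.5 times to 40/10 = 4 times. The dose would be 10 mg or less only at 10/0.5 = 20 kg or below, which is not an adult weight. Criterion 25 concerns escalating or chronic use, so it is only a benchmark. It shows that the physiologic-dose approval does not clearly cover this course.

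**Step 5. Denominators.** Section 9.4.3.1 divides responders by all treated patients, and the safety population is everyone who took a dose. Removing a patient after treatment has started changes neither.

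**The case against.** The best case on the other side has four parts.

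1. *The rash row may not be purely non-immune.* Just above the table, Section 6.6.1 reports rash or pruritus and raised liver tests with a related drug class, then sends other irAEs to a separate table. The irAE table in Section 6.6.2 has no skin row, only a catch-all. The Grade 3 rash row itself mentions Stevens-Johnson syndrome and toxic epidermal necrolysis, which a footnote to the irAE table also lists. On this reading some of the directed prednisone already falls within Section 6.5's exception. This stands as real ambiguity and is why confidence is medium. It does not remove the conflict, because the heading and the Grade 2 routing point the other way.
2. *Suspicion alone lifts the ban.* Section 2.3 lists rash as an expected irAE, so many severe rashes will qualify. This stands and narrows the scope. It does not help the patient whose rash is judged non-immune.
3. *Section 6.5 can be read as permissive.* It says discontinuation may be needed, provides for continuation by agreement, and says patients should, not must, be removed. Sections 7.1 and 7.2 do not list steroid need as a reason to stop. So a reader who infers that removal is compulsory goes further than the text. What remains is that a step the toxicity table treats as routine becomes a negotiation.
4. *Recurrent Grade 2 rash.* A reader might infer that "for recurrent Grade 2, or toxicity lasting more than 2 weeks proceed as Grade 3" brings the prednisone with it. That phrase is in the column for action on study drug, and the Grade 2 management cell lists only an oral antibiotic and a topical steroid. The text does not clearly direct prednisone there, so recurrent or prolonged Grade 2 rash is left out of this point.

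**Conclusion.** The inconsistency is real: for Grade 3 acneiform rash not suspected to be immune and improving within two weeks, the toxicity table says treat and restart while Section 6.5 says remove, and nothing states which governs. It is minor, with medium confidence. No incidence is given, so the number of patients affected is unknown and may be very small. The conclusion assumes that the Grade 3 row applies to non-immune rash, as its heading says, and that the blacked-out text in Section 6.5 contains no exception for it.

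Two larger consequences might be inferred, and the documents do not support either as a general effect.

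- *Loss of survival data.* Note b to the schedule of activities ends long-term follow-up at study withdrawal. But Section 7.1 says stopping treatment is not withdrawal, and the opening of Section 7 keeps patients who discontinue in scheduled follow-up. Survival data are at risk only if removal is taken literally.
- *A distorted recommended Phase 2 dose.* The dose is chosen on the totality of data, and the rash itself is still reported. At most, some reduced-dose experience is lost in a small subset.

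**What to change.** In both steroid sentences of protocol Section 6.5 (the narrative prohibition and the entry in the list of restrictions), add: *or as directed for toxicity management in Section 6.6.1; such use does not require removal from the study*.

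Leave the removal sentence as it is for the other listed restrictions, such as chemotherapy, other immunotherapy, investigational agents, radiation and live vaccines. Rewriting it for all of them would change rules that this point does not examine.

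The cost is one clause in two sentences, with no new data, visits or procedures and no change to the analysis.
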